Screening/Washout Visits	
Subjects with an ophthalmic history of increased IOP (≥ 22mmHg and ≤ 30 mmHg) will be selected for study participation and be screened for study eligibility.
 
After Screening, eligible subjects, if currently being treated with glaucoma medications, will be required to washout and refrain from administration of any glaucoma drugs for at least 28 days and no more than 35 days prior to the Qualification Visit. The washout subjects will be brought back at approximately two weeks after starting the washout period for an IOP safety check. In the judgement of the investigator, if there is any risk to the eye(s) of the subject, or if the mean IOP in either eye during washout is >30mmHg, then an appropriate rescue or prior medication will be administered, and the subject will be considered a screen failure. Adverse events occurring during the washout period will also be assessed at this visit.
 
Subjects not previously treated with any glaucoma drugs will not require a washout period and may return the following day or up to 35 days later for their Qualification/Baseline Visit.

Qualification/Baseline Visit	
After the washout, where applicable, a Qualification Visit will occur before dosing on Day 1.
 
At the Qualification Visit, IOP eligibility will be determined with [REDACTED] at 8AM, 10AM, and 4PM (mean IOP at 8AM must be ≥ 22mmHg and ≤ 30mmHg, and ≥ 19 mmHg at 10AM and 4PM). IOP will be measured twice in both eyes at each timepoint and the mean value will be used in eligibility assessments. All IOP measurements have a window of ± 15 minutes with at least 2 hours between the 8AM and 10AM assessments.
 
The eye with the higher IOP at the Qualification Visit at 8AM is designated as the study eye for the primary endpoint efficacy analysis. In the case where both eyes have the same IOP, the study eye will be the RIGHT eye. ALL TREATMENTS WILL BE ADMINISTERED TO BOTH EYES (OU).
 
If the subject meets all eligibility criteria, then the Qualification Visit is the Baseline Visit. The subject will then be randomized into the study.
 
The first dose of study medication will be taken at 8PM to 10PM on the Baseline Visit (Day 1).

Treatment-study Visits	
Treatment-study visits will occur twice - on Day 8 ± 1 Day and Day 15 ± 1 Day. IOP evaluations will be performed at 8AM,

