7.2.3. Qualification Visit/Baseline (Day 1)

At the Qualification/Baseline Visit, the subject will be asked how do his/her eyes feel, and if there have been any changes in their medical condition, or concomitant medications since their last visit. Any adverse changes in the condition of the subject at this visit are recorded in the Medical/Ophthalmic History CRF.

At the Qualification/Baseline Visit:

- Females of childbearing potential will take a urine pregnancy test at 8AM.
- Review of concomitant medications at 8AM.
- IOP measurements using a [REDACTED] at the Baseline visit and both Treatment-study visits will be done at 8AM, 10AM and 4PM. All IOP measurements have a window of ± 15 minutes with at least 2 hours between the 8AM and 10AM assessments. IOP will be measured twice in both eyes at each timepoint. The mean value at each timepoint for the study eye will be used in efficacy assessments. If the difference in the two IOP measurements is >5 mmHg, a third measurement will be obtained, and the three values averaged.
- Pupil diameter, using a [REDACTED], near visual acuity using a standard chart held at 14 inches and distance visual acuity with ETDRS are measured at 8AM.
- Resting HR and BP are measured at 8AM and 4PM. Blood pressure, using the same arm, same cuff size appropriate for arm circumference throughout the study, and heart rate should be measured after at least 3 minutes rest in the sitting position. If HR or BP are outside the normal range (see Exclusion Criteria – Systemic #7 and #8), they may be repeated only once following at least a 5 minute rest period in the sitting position.
- Eye redness (conjunctival hyperemia) visually checked at 8AM, 10AM and 4PM using [REDACTED]
- Adverse events will be reviewed at each timepoint.

To continue in the study, the subject must have a mean IOP ≥ 22 mmHg at 8AM and ≥ 19 mmHg at 10AM and 4PM in the study eye **after the washout period** (if required) at the Qualification Visit (8AM).

Subjects may qualify in either eye. The eye with the higher IOP at the Qualification Visit at 8AM is designated as the study eye for the efficacy endpoints. In the case where both eyes have the same IOP, the study eye will be the RIGHT eye. See Section 9 for more information on statistical analysis. ALL TREATMENTS WILL BE ADMINISTERED TO BOTH EYES (O.U.).

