8. ASSESSMENT OF SAFETY

8.1. *Specification of safety parameters*

The assessment of safety and tolerability is the secondary objective of this study. The assessment of safety will be evaluated by:

- Conjunctival hyperemia measured with a [REDACTED]
[REDACTED]
[REDACTED]
[REDACTED]
[REDACTED]
- Biomicroscopy of anterior segment including evaluation of cornea, conjunctiva and anterior chamber. Fluorescein staining to be used.
- Ophthalmoscopy. Dilated fundus exam including optic nerve, macula, vessels and periphery.
- Heart rate and blood pressure. Blood pressure should be measured using the same arm and same cuff size appropriate for arm circumference throughout the study. BP and heart rate should be measured after at least 3 minutes rest in the sitting position. If HR or BP are outside the normal range (see Exclusion Criteria – Systemic #7 and #8), they may be repeated only once following at least a 5 minute rest period in the sitting position.
- Adverse events.

8.2. *Assessing, recording, and analyzing safety parameters*

The timing for recording safety parameters may be found in Section 4.2, [Table 1: Schedule of Visits and Procedures](#).

8.3. *Adverse events*

All AEs and SAEs that occur following consent and until the final study visit should be collected and recorded on the AE or SAE CRF page. Only treatment-emergent adverse events/adverse reactions will be summarized (see Section 9.3.5).

All treatment-emergent adverse events/adverse reactions occurring during the study (i.e. once the subject has received one dose of study medication) **must** be documented, regardless of the assumption of causal relationship, on the respective CRF. All treatment-emergent adverse events/adverse reactions must be documented from the time the subject receives the **first dose** of study medication until the subject's participation in the study has been completed. If a subject has ongoing adverse events/adverse reactions at the time of study completion, the ongoing adverse events/adverse reactions **must** be followed-up and provided appropriate medical care until the signs and symptoms have remitted or stabilized or until abnormal laboratory findings have returned to acceptable or pre-study limits.

Documentation of adverse events/adverse reactions includes start date and stop date, severity, action(s) taken, seriousness and outcome.

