9.3.5. Analysis of Safety

No statistical analysis of safety data will be performed in this study. Safety will be assessed using the SP with subjects included in the treatment group they actually received, regardless of their randomized treatment. Observed case data will be used; no imputation will be performed for missing safety data.

For all safety endpoints, Baseline is defined as the pre-dose value from the Baseline Visit/Day. If there is no pre-dose value from Day 1, then Baseline will be the value from the Screening Visit.

Biomicroscopy results, and ophthalmoscopy results will be summarized by treatment group using the SP. As both eyes are treated in the study; both eyes will be included in the summarizations for visual acuity, biomicroscopy, and ophthalmoscopy. Separate summary tables will be created for the study eye versus the fellow eye.

Heart rate and blood pressure values and change from Baseline in the values will be summarized by treatment group and timepoint (8AM on Day 8, Day 15 and Day 16; 4PM on Day 15).

Verbatim descriptions of AEs will be coded using MedDRA. Only treatment-emergent AEs (TEAEs; those that occur after the first dose of study medication *or increasing in severity after initiation of study medication*) will be summarized. TEAEs and serious AEs (SAEs) will be summarized by treatment group, by system organ class (SOC), severity, and relationship to study medication. Deaths, withdrawal from study medication due to AEs, and withdrawal from the study due to AEs will each be summarized by treatment group. Note that in MedDRA, ocular events are coded to the SOC of “special senses”. Thus, using SOC in the summaries will provide a separation of ocular and non-ocular adverse events.

All safety data will be provided in by-subject listings.

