#### **7.6. Baseline Values**

Baseline values are the values obtained prior to the first study drug administration on Day 1 (scheduled between 8PM and 10PM in the evening). If the Day 1 value is missing, the value at Screening will be treated as the baseline.

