### **10.1. Adverse Events**

Adverse events will be coded using MedDRA, Version 22.0.

Treatment-emergent adverse events (TEAEs) are defined as any adverse event that begins or worsens after initiation of the investigational product and through the subject's last study visit (study completion or early termination) or follow-up telephone call. Serious adverse events will be recorded from the date of informed consent, throughout the clinical trial.

If the onset of an AE is on or after the date of first dose of study medication, or increasing in severity after first dose of study medication, then the AE will be considered treatment-emergent.

Only TEAEs will be summarized; all AEs (TEAE, non-TEAE) will be included in a by-subject listing.

The number and percent of subjects with any TEAEs will be summarized by system organ class and preferred term by treatment group and overall. At each level of tabulation (ex. at the preferred term level) subjects will be counted only once if they had more than one such event reported during the AE collection period.

Note that in MedDRA, ocular events are coded to the SOC of “special senses”. Thus, using SOC in the summaries will provide a separation of ocular and non-ocular adverse events.

The following summary tables will be presented for TEAE data:

- Overall summary of TEAEs
- Summary table of TEAEs by SOC and PT
- Summary table of TEAEs by highest relationship level to study drug by SOC and PT (not related, possibly related, related)
- Summary table of TEAEs by maximum severity by SOC and PT (mild, moderate, severe)
- Summary table of serious TEAEs by SOC and PT
- Summary table of TEAEs leading to withdrawal from the study by SOC and PT
- Summary table of TEAEs leading to study medication discontinuation by SOC and PT

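### SAP 10.1 defines treatment-emergent events by sequence but classifies them by date, so an adverse event recorded on Day 1 before the evening dose counts as treatment-emergent (minor)

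*SAP*

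**What the plan says.** SAP 10.1 (Adverse Events) gives two rules in consecutive paragraphs. The definition is by sequence: "any adverse event that begins or worsens after initiation of the investigational product". The rule that would be programmed is by calendar date: "If the onset of an AE is on or after the date of first dose of study medication", or if severity increases after that dose, the event is treatment-emergent.

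The protocol uses sequence throughout. Its Analysis of Safety section takes TEAEs as "those that occur after the first dose of study medication", plus events that become more severe once treatment has started. Section 8.3 likewise starts the treatment-emergent period when the subject has received a dose. SAP 3.3 states that the SAP's analyses agree with the protocol.

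The Day 1 timetable comes from the Protocol Study Summary, Protocol 7.2.3 and SAP 7.6. The visit has assessments at 8AM, 10AM and 4PM, and the first dose follows at 8PM to 10PM. Protocol 7.2.3 says of this visit: "Adverse events will be reviewed at each timepoint".

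The protocol gives two instructions on where a Day 1 finding is written down. Section 7.2.3 says: "Any adverse changes in the condition of the subject at this visit are recorded in the Medical/Ophthalmic History CRF". Section 8.3 says: "All AEs and SAEs that occur following consent and until the final study visit should be collected and recorded", on the adverse event or serious adverse event page.

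**The concern.** A date rule does little harm when the first dose is taken early in the day. Here most of Day 1 passes before any drug is given. In that time the subject has repeated applanation tonometry in both eyes, has redness checked three times, and practises instillation with artificial tears. These procedures could plausibly cause mild irritation or redness, and conjunctival hyperemia is the event most often reported with this drug (Protocol 8.3.1).

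Adverse events are a primary safety measure. Only TEAEs are tabulated, and no statistical tests of safety are planned, so the TEAE counts are what a reader of the safety tables will compare. There is also an internal inconsistency: SAP 7.6 treats Day 1 values before the dose as baseline. Redness that first appears at 4PM and is entered as an adverse event would therefore be both a baseline finding and a TEAE. Two programmers working from SAP 10.1 could produce different tables.

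**Working it through.** The plan states no figure on this point that could be reproduced. The check compares the rules and adds clock arithmetic.

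**Inputs.** First dose at hour 20 to 22 of Day 1 (Protocol Study Summary; SAP 7.6). Adverse event reviews at hours 8, 10 and 16 (Protocol 7.2.3). About 40 subjects randomized 1:1, so 40 / 2 = 20 per arm. Follow-up to Day 22.

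**The two rules applied to an event entered as an adverse event**

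| Event | SAP and protocol definition (sequence) | SAP date rule |
|---|---|---|
| Onset before Day 1, no worsening | Not a TEAE | Not a TEAE |
| Onset on Day 1 before the dose, no worsening | Not a TEAE | **TEAE** |
| Onset on Day 1 before the dose, worse afterwards | TEAE | TEAE |
| Onset on Day 1 after the dose | TEAE | TEAE |
| Onset on Day 2 or later | TEAE | TEAE |

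The rules differ in the second row only.

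**Length of the window**

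- 8AM visit start to dose: 20 − 8 = 12 h; 22 − 8 = 14 h.
- Last scheduled review (4PM) to dose: 20 − 16 = 4 h; 22 − 16 = 6 h.
- Share of the Day 1 date that is before the dose: 20/24 = 83%; 22/24 = 92%. The remaining 2 to 4 hours are after it.
- Share of a Day 1 to Day 22 date window: 20/(22 × 24) = 3.8%; 22/(22 × 24) = 4.2%.

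**Which events reach the second row.** Only those entered as adverse events. Events found at the visit go to the history form under Protocol 7.2.3 and to the adverse event form under 8.3, so the number depends on which instruction a site follows. Events that start between the 4PM review and the dose are also exposed. In addition, SAP 7.3.2.1 sets an unknown start day in the month of first dose to the first-dose day, and the date rule then makes such an event a TEAE.

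**Can the sequence rule be applied?** Protocol 8.3 lists start and stop dates for each event and mentions no clock time. The case report form is not in the documents, so whether it captures onset time is unknown.

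**Effect on an arm's rate.** One misclassified subject with no other TEAE adds 1/20 = 5 percentage points. A subject who has another TEAE adds nothing to the overall rate.

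**Effect on the contrast.** Suppose a share q of subjects in each arm has such an event, independently of having a true TEAE. Each true rate p becomes p + q(1 − p), and the difference between arms is multiplied by (1 − q). The documents give no adverse event rate, so q is an assumption. With 1 or 2 of 20 (q = 5% or 10%), an illustrative 30-point difference becomes 30 × 0.95 = 28.5 or 30 × 0.90 = 27 points.

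**The case against.** The strongest reply is that this is a mismatch of wording with little consequence, and much of that reply stands.

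- **Every Day 1 complaint becomes a TEAE.** A reader might infer this, but the documents do not support it. Protocol 7.2.3 sends adverse changes at this visit to the history form, whereas the instructions for Days 8, 15, 16 and 22 make changes adverse events. Protocol 8.3.1 also keeps a pre-dose condition that is unchanged or improved from being recorded as an adverse event later. This narrows the exposure. It does not remove it, because Section 8.3 sends all events after consent to the adverse event form.
- **Pre-dose events are blamed on the drug.** This is also tempting and also unsupported. Treatment-emergent is a class of timing. The investigator judges relationship separately, and SAP 10.1 tabulates it with a not-related category.
- **The comparison is tilted towards one arm.** It is not, in expectation. Randomization follows all three Day 1 IOP assessments, and events between then and the dose occur under masked allocation before any drug. Chance imbalance remains possible with 20 per arm.
- **Redness is covered elsewhere.** SAP 10.3 summarizes graded redness by timepoint, whatever the TEAE classification. This protects the most likely example, but not other ocular complaints.
- **With dates only, an inclusive rule is sensible.** It avoids losing true reactions in the 2 to 4 hours after the dose. That is right for events of unknown order, and the fix keeps it. It does not justify counting events known to precede the dose.
- **Nothing is hidden.** All adverse events are listed by subject. However, the listing does not correct the tables.

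**Conclusion.** The contradiction is real. The date rule in SAP 10.1 departs from the definition just above it and from the protocol, and it makes a TEAE of any pre-dose Day 1 event that is entered as an adverse event and does not worsen. The number of such events cannot be computed from the documents and is probably small. The effect is at most 5 percentage points on an arm's overall rate for each affected subject, assuming about 20 per arm and no other TEAE in that subject. The expected result is modest inflation in both arms with slight dilution of the difference. Severity is minor. The point is worth correcting because these are the only adverse event tables planned and the correction is cheap.

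**What to change.** In SAP 10.1 keep one rule: a TEAE is an adverse event with onset or worsening after the first dose. Replace the date sentence with a rule for Day 1 onsets.

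- Class the event as non-TEAE when the recorded onset time, a flag for before or after the first dose, or the visit timepoint at which it was reported shows that it began before the dose, and it did not worsen afterwards.
- Class it as a TEAE when it began after the dose or when the order is unknown. State this default openly. A start day imputed to the first-dose day under SAP 7.3.2.1 counts as unknown order unless other information settles it.
- From Day 2 onward, dates are sufficient.

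Separately, reconcile Protocol 7.2.3 with 8.3 on where Day 1 pre-dose events are recorded, so that sites do not differ.

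The cost is a short change to the SAP before unmasking, a little extra data handling and, if the case report form captures neither onset time nor order, one added item. The change makes no difference for Day 1 events whose order cannot be established.

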## **10.2. Deaths, Serious Adverse Events and Other Significant Adverse Events**

### **10.2.1. Deaths**

The AE listing will include all AEs, including deaths, regardless of causality; one of the columns in the listing will specify whether the AE was fatal.

Clinical narratives for each death will be written to include important data and safety findings related to the individual death and included in the final clinical study report.

### **10.2.2. Serious Adverse Events**

The AE listing will include all AEs, including serious adverse events (SAEs); one of the columns in the listing will specify whether the AE was an SAE.

Clinical narratives for each SAE observed will be written to include important data and safety findings related to the individual SAE and included in the final clinical study report.

### **10.2.3. Adverse Events Leading to Withdrawal from the Study**

The AE listing will include all AEs, including AEs leading to withdrawal from the study; one of the columns in the listing will specify whether the AE led to withdrawal from the study.

### **10.2.4. Adverse Events Leading to Discontinuation of Study Medication**

The AE listing will include all AEs, including AEs leading to discontinuation of study medication; one of the columns in the listing will specify whether the AE led to discontinuation of study medication.

## **10.3. Biomicroscopic and Ophthalmoscopic Examinations**

Results from biomicroscopic examinations, including conjunctival redness, cornea, conjunctiva (other than redness), anterior chamber, and corneal fluorescein staining will be summarized descriptively for each treatment group and overall by time point for the observed value. Results from ophthalmoscopic examinations, including optic nerve, macula, vessels and periphery will be summarized similarly. Separate summaries will be created for the study eye and the fellow eye.

For conjunctival redness, a descriptive summary of the numeric values from the CCLRU card 4-point scale will also be summarized by treatment group and overall by time point.

All examination data will be presented in by-subject listings. Unscheduled examinations will not be summarized but will be included in the listings.

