2. INTRODUCTION

2.1. *Investigational products*

The test product is Nyxol Eye Drops - 1% phentolamine mesylate ophthalmic solution (Nyxol), an alpha-1-adrenergic antagonist. Placebo control is Nyxol vehicle alone.

2.2. *Findings from nonclinical and clinical studies*

Detailed findings from nonclinical and clinical studies and potential risk are provided in the Investigators' Brochure (IB) (January 2019).

Single Dose Phase 2:

In NYX-SNV, treatment of 16 subjects with severe night vision disturbances with a single dose of 1% Nyxol resulted in [REDACTED]

Statistically significant improvements in several measurements of visual function as well as wavefront aberrometry were also reported. Modest, transient increases were seen in conjunctival and bulbar hyperemia.

Multiple Dose Phase 2:

In NYX-01a2, (Ocularis IND 70-499) 60 otherwise healthy subjects with reduced mesopic contrast sensitivity (CS), divided into three groups of twenty subjects each, received placebo, 0.5% or 1.0% Nyxol for 15 days, followed by an optional two week period where the subjects could use up to six doses of 1.0% Nyxol as needed.

IOP was measured 2 hours after the first dose on Day 1, and then again on Day 32 that was at least three days after the last dose. The mean absolute IOP and mean IOP changes post treatment on Day 1 were statistically significant between the treatment arms and the placebo arm.

[REDACTED]

More than 100 subjects have received active doses of Nyxol ranging from 0.2% to 1.0% in Phase 1 and Phase 2 clinical trials. There have been no serious adverse events. All treated subjects developed some degree of conjunctival hyperemia, an average of one point increase on a four point CCLRU scale (none, mild, moderate, severe). Most subjects went from mild to moderate. Three went from mild to severe. All redness resolved within 8 hours.

The anticipated benefits of the proposed study are reduction in IOP and improvement in the signs and symptoms of open angle glaucoma and ocular hypertension. The risks determined in previous ophthalmic studies are local hyperemia and conjunctival injection.

Systemic risks, principally tachycardia and hypotension, are known from parenteral administration of doses of 5 mg phentolamine mesylate (Regitine, Bedford, Ohio; see Regitine

Prescribing Information in IB) and local injectable administration of OraVerse (Novalar, San Diego, California; see OraVerse Prescribing Information in IB).

Design justification

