### **4.2. Study Endpoints**

#### **4.2.1. Primary Endpoints**

The primary efficacy endpoint from the protocol is the change from Baseline to Day 15 in mean diurnal IOP in the study eye. Mean diurnal IOP is the mean of the IOP measurements at all three timepoints (8AM, 10AM, 4PM).

The primary safety measures are:

- Objective biomicroscopic and ophthalmoscopic examination
- Subjective ocular tolerability
- Adverse events (AEs)

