## **10.4. Vital Signs**

Descriptive statistics of observed values will be presented for vital sign data by time point, including systolic BP (mmHg), diastolic BP (mmHg), and HR (bpm) by treatment group. Changes from baseline to each scheduled post-baseline visit and timepoint will be presented.

All vital sign data will be presented in a by-subject listing. Unscheduled visit or repeated results will not be summarized but will be included in the listings.

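### SAP 10.3 tabulates the eye examinations and redness grades only as observed values, so these tables cannot show how many eyes worsened from Baseline

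*SAP*

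**What the plan says.** SAP Section 4.2.1 lists the primary safety measures, the first being "Objective biomicroscopic and ophthalmoscopic examination". SAP Section 10.3 gives their analysis. Biomicroscopy results, with redness among them, "will be summarized descriptively for each treatment group and overall by time point for the observed value". For the fundus, "Results from ophthalmoscopic examinations, including optic nerve, macula, vessels and periphery will be summarized similarly". For redness there is one addition: "a descriptive summary of the numeric values from the CCLRU card 4-point scale will also be summarized by treatment group and overall by time point". Study eye and fellow eye are summarised separately, and all examination data are listed by subject.

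Protocol Section 9.3.5 (Analysis of Safety) likewise names only summaries by treatment group and by eye for these examinations. The same section says "For all safety endpoints, Baseline is defined as the pre-dose value", with the Screening value as fallback; SAP Section 7.6 repeats that fallback.

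Vital signs are treated differently. The protocol plans both values and change from Baseline for heart rate and blood pressure, and SAP Section 10.4 says "Changes from baseline to each scheduled post-baseline visit and timepoint will be presented".

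**The concern.** A table of observed grades by visit treats an eye graded moderate on Day 15 the same whether it started at none or at moderate. Safety readers will want to know how many eyes got worse on Nyxol and how many on placebo. Vital signs, which the protocol places among its other safety measures, get a within-subject summary; the primary ocular examinations do not.

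The gap matters most for redness, the best-known ocular effect of the drug. Protocol Section 2.2 describes earlier results as movement from a starting grade that was not zero: "Most subjects went from mild to moderate. Three went from mild to severe". The tables planned in SAP 10.3 could not produce that kind of statement for this trial. Optic nerve findings are a similar case: the trial enrols subjects with open angle glaucoma and excludes only damage judged too severe for washout, so some findings may be present before dosing.

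**Working it through.** **Arm size.** The protocol and SAP sample size sections give 36 completers, about 10% drop-out and 1:1 allocation. 36 / (1 − 0.10) = 40, which reproduces the stated total, and 40 / 2 = 20 per arm. Because the two eyes are tabulated separately, each arm's study-eye table has about 20 eyes.

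**What visit counts determine.** Observed-value tables give the margins of a Baseline-by-visit cross-table. The number of worsened eyes lies in the interior of that cross-table. The counts below are assumptions for illustration; the documents give none for this trial.

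*Redness, grades none/mild/moderate/severe, 20 eyes:*

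| Baseline | Day 15 | Eyes worsening by at least 1 grade |
|---|---|---|
| 6/10/4/0 | 6/10/4/0 | 0 to 10 |
| 6/10/4/0 | 4/9/6/1 | 3 to 13 |

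- Row 1, lower limit: nobody changes, 0.
- Row 1, upper limit: an eye that worsens into mild must start at none (at most 6), and at most 4 eyes end at moderate, so 6 + 4 = 10. This is attainable: 6 none to mild, 4 mild to moderate, 6 mild to none, 4 moderate to mild.
- Row 2, lower limit: eyes at moderate or above rise from 4 to 6 + 1 = 7, so at least 7 − 4 = 3 must have worsened. This is attainable: one none to severe, one none to moderate, one mild to moderate.
- Row 2, upper limit: at most 6 eyes can worsen into mild, 6 end at moderate and 1 at severe, so 6 + 6 + 1 = 13.

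*Finding recorded as normal or abnormal:* with b of n eyes abnormal at Baseline and f at the visit, the number newly abnormal lies between max(0, f − b) and min(f, n − b). For n = 20:

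- b = 10, f = 10: 0 to 10
- b = 5, f = 5: 0 to 5
- b = 10, f = 12: 2 to 10
- b = 0, f = 5: exactly 5

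Visit counts fix the answer in the last case because no eye has the finding at Baseline.

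**What the tables do determine.** With complete data, the difference between visit means equals the mean change. Scoring the grades 0 to 3 (an assumption; any coding with unit steps gives the same difference), the Baseline mean is (10 + 2×4)/20 = 0.9. For 4/9/6/1 the Day 15 mean is (9 + 2×6 + 3×1)/20 = 1.2. Mean change is 0.3, and it is compatible with 3 to 13 eyes worsening.

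**Whether the paired data exist.** For redness, yes. Protocol Section 7.2.3 has it graded at 8AM, 10AM and 4PM at Baseline; Sections 7.2.4 and 7.2.5 repeat it at each timepoint on Days 8 and 15; Section 7.2.6 adds Day 16, an 8AM visit. For the other examinations the pairing is less clear. Protocol Section 7.2 says in general terms that eye examinations are done at Baseline, but the readable list in 7.2.3 names no biomicroscopy. Section 7.2.1 places it at Screening and 7.2.5 at 4PM on Day 15. Under the fallback rule, the Screening value may therefore serve as Baseline.

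**The case against.** The strongest reply is that worsening already has its own route. Protocol Section 8.3.1 keeps unchanged or improved pre-existing conditions out of the adverse event record. Sections 7.2.4 to 7.2.7 have changes in condition recorded as adverse events, and SAP Section 10.1 counts events that begin or worsen after first dose, by severity and relationship. All examination data are listed. This stands: a reader might infer that the plan as a whole cannot tell new findings from old ones, and the documents do not support that.

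It does not fill the gap in the tables. No readable text ties a change in examination grade to an adverse event. The redness terms in Section 8.3.1 turn on whether redness persists 2 hours after instillation, whereas dosing is at 8PM to 10PM and clinic grading starts at 8AM, 10 to 12 hours later. SAP 4.2.1 also lists the examinations and adverse events as separate primary measures. Listings hold the information, but a reader would have to build the shift table by hand.

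A reader might also infer lost precision. That is not supported. Safety is descriptive, with no test or interval planned. Any gain depends on a Baseline-to-visit correlation r that the documents do not give: with equal variances, the ratio of standard errors (change to observed) is √(2(1 − r)), which is 1 at r = 0.5 and above 1 below it.

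Nor do the two documents conflict. The protocol asks for change from Baseline only for heart rate and blood pressure, and the SAP follows it. No figure shows that many subjects will be recently washed out: untreated subjects are eligible and skip washout. Starting redness has support only from earlier studies in other populations.

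**Conclusion.** The point holds for the examination tables. In the readable text of SAP 10.3, a primary safety measure is reported without any within-eye comparison, although a Baseline is defined and, for redness, time-matched pairs are collected. The number of eyes that worsened is not recoverable from those tables: 0 to 10 of 20 in the unchanged-margins example, 3 to 13 in the other. Both ranges rest on assumed counts, and the ambiguity disappears only where no eye has the finding at Baseline.

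The size is modest. Group-level redness change is visible if Baseline is among the tabulated time points, adverse events and listings carry worsening separately, and no planned inference is affected. The list of planned tables is redacted, so a shift table named only there cannot be excluded; if there is one, the text of 10.3 should still say so. The change is worth making because it directly serves the ocular safety objective at very little cost.

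**What to change.** In SAP Section 10.3 add, by arm and separately for study eye and fellow eye:

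- **Redness:** a shift table from Baseline, the number and percentage of eyes worsening by at least 1 and at least 2 CCLRU grades, and the mean change. Match each reading by clock time to the 8AM, 10AM and 4PM Baseline gradings (8AM for Day 16).
- **Biomicroscopy and ophthalmoscopy:** a shift table from Baseline to each scheduled post-dose examination, using the categories collected. Grade-step counts are not proposed here, because redness is the only examination with a visible graded scale.
- **Baseline:** state which pre-dose examination counts as Baseline for each measure, and say so if it is the Screening examination.

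The cost is a few extra descriptive tables from data already collected. No new assessment and no change to study conduct is needed.
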